- **Group 2:** Standard of care plus Battlefield acupuncture at treatment sites Cingulate gyrus, thalamus, omega 2, shen-men, point zero in both ears (see figures 1-5). The 5 needles will remain in each ear for up to 7 days or allowed to fall out on their own (the patient will be instructed not to remove the needles).
 - Subject's ears will be cleansed with an alcohol swab
 - Subjects will be given a handout of standard BFA Discharge Instructions including what an infection looks like and what to do in the event of an infection (see attached).

Visit 1: Will occur after a minimum of 6 hours post vaginal birth (up until hospital discharge) to avoid disturbing maternal infant bonding or a minimum of 24 hours post caesarean section to avoid confounding with the anesthesia:

- Subject will be given treatment according to their randomization group.
- All subjects, regardless of randomization group, will be instructed to have no heavy meals, no excessive hot or cold foods, no heavy exercise or intercourse, and no alcohol for 6 hours.
- Satisfaction with post-partum pain management will be assessed with the following questions:
 - On a scale of 0 to 10, how satisfied were you with your pain management after delivery? (dissatisfied 0 – 10 very satisfied)
 - Would you use auricular acupuncture for future pain management? (Yes or no) (for those in the acupuncture group only)
 - On a scale of 0-10, with 10 being the worst pain, what is your level of pain?

In hospital data collection:

Data will be collected each day until the patient has been discharged from the hospital. Subjects will be contacted either in person or via phone and the hospital stay will vary from patient to patient:

- We will review the subject's medical record and record RN Recorded Pain assessments, Delivery method (either Caesarean section or spontaneous vaginal delivery), Delivery complications (vaginal lacerations, use of episiotomy, operative vaginal delivery, shoulder dystocia, post-partum hemorrhage), Birth weight, Maternal Parity, and record what pain medications they are taking.
- We will ask subjects if they prefer to be contacted in-person or via telephone while in the hospital.
- Satisfaction with post-partum pain management will be assessed with the following questions:
 - On a scale of 0 to 10, how satisfied were you with your pain management after delivery? (dissatisfied 0 – 10 very satisfied)
 - Would you use auricular acupuncture for future pain management? (Yes or no) (for those in the acupuncture group only)
 - On a scale of 0-10, with 10 being the worst pain, what is your level of pain?
 - Are the needles still in place? If yes, how many in each ear?

Post hospital discharge:

Each day up until 10 days post Visit 1. Subjects will be contacted phone and the following information will be collected:

[figure not shown]
- Satisfaction with post-partum pain management will be assessed with the following questions:
 - On a scale of 0 to 10, how satisfied were you with your pain management after delivery? (dissatisfied 0 – 10 very satisfied)
 - Would you use auricular acupuncture for future pain management? (Yes or no) (for those in the acupuncture group only)
 - On a scale of 0-10, with 10 being the worst pain, what is your level of pain?
- We will record what pain medications they are taking including drug name, strength, and total doses since discharge from the hospital.

Placement of Battlefield Acupuncture:

Battlefield auricular acupuncture utilizes up to 10 needles (see figure 6). The ear Acupuncture points include Cingulate gyrus, thalamus, omega 2, shen-men, point zero (see figures 1-5). The subject will receive five needles on each ear. Intermittent placement checks by the medical acupuncturist will be performed.

The acupuncture being performed in this study is a standard acupuncture technique for the treatment of pain. The physicians performing the treatment are trained in this acupuncture technique. As such, all physicians trained in this procedure will be able to perform the acupuncture for treatment of research subjects.

The Food and Drug Administration (FDA) regulates acupuncture needles as a class II medical device, because they are intended for use in the cure, mitigation, treatment, or prevention of disease in man or are intended to affect the structure or function of the body of man. The FDA regulates the acupuncture needles (see 21 CFR 880.5580), but not the practice of acupuncture itself. The needles being used are Sedatelec ASP Original Gold needles, which are exempt from premarket notification by the FDA for use in acupuncture and will be used in accordance with their FDA approved labeling.

3.6.1. Interventions, Observations, or Data Sought:

We will review the subject's medical record and record the following standard of care items: RN Recorded Pain assessments, delivery method (either Caesarean section or spontaneous vaginal delivery), delivery complications (vaginal lacerations, use of episiotomy, operative vaginal delivery, shoulder dystocia, post-partum hemorrhage), birth weight, and maternal parity. Before discharge, we will also assess the patient's satisfaction with her post-partum pain control via a short questionnaire as detailed above. After delivery of the battlefield acupuncture and the first post-hospital discharge day, the patient will be contacted by the research coordinators and assessed on their overall pain scale (scale of 0 to 10) and the amount of pain medicines utilized over the past 24 hours. Post-hospital discharge follow-up will continue for up to 10 days post Visit 1 for each study group.

3.6.2. Data Collection and Processing:

Data will be collected and recorded in a spreadsheet. At the conclusion of the study, all personally identifying information will be removed prior to analysis based on AFI 33-332, "The Air Force Privacy and Civil Liberties Program" and the "National Institute of Standards and Technology Special Publication (NIST SP 800-88) for the approved methods to destroy PII". Each subject will be asked to place their de-identified study-related data into the "Nellis Acupuncture Research Data Repository (FWH20140048H)" for future research. If the subject does not give their authorization, then all de-identified study-related data will be destroyed no later than at the closure of the study.

3.6.3. Setting:

Post-partum females (DoD beneficiaries), age 18 years or older, at the Mike O'Callaghan Military Medical Center. No other special populations (e.g., children, military basic trainees, prisoners, detainees) will be recruited.

3.6.4. Date(s):

June 2015 through June 2017

3.6.5. Source of Research Material:

Source of Research Material per Participant (Procedures)	# Routine Care	# Research Driven	# Total Procedures
Medical Record review	0	2	2
Acupuncture	0	1	1
Questionnaire	0	Up to 11	Up to 11

3.6.6. Subjects:

Post-partum females (DoD beneficiaries), age 18 years or older, will be recruited at the Mike O'Callaghan Military Medical Center. No other special populations (e.g., children, military basic trainees, prisoners, detainees) will be recruited.

3.6.7. Inclusion/Exclusion Criteria:

Inclusion:

- Post-partum female (DoD beneficiaries).
- Age 18 years or older
- Pain score rating post-delivery of greater or equal to 4/10.

Exclusion:

- Absence of one or more ears

- Active cellulitis of ear
- Ear anatomy precluding identification of acupuncture landmarks
- Non-English speaking
- Use of Hearing Aids that preclude the use of ear acupuncture
- Known allergy to gold

3.6.8. Instrumentation: N/A

4.0. Human Subject Protection:

4.1. Recruitment:

All potentially eligible patients will be offered an opportunity to participate. Primary Care Managers (PCMs) who are not part of the research team will be informed about the study and provided information on the inclusion/exclusion criteria. PCM referrals and posted advertisements will be utilized for recruiting subjects to the study. Some patients may be patients of the PI or AI, however, they will have the study staff recruit their patients to prevent any misconception of coercion or undue influence. If a potential subject is identified by the treating PCM and is interested in obtaining more information about the study, the patient will either be provided a contact number to the Research Staff, the Research Staff will be given the potential subject's contact information by the PCM with the patient's oral or written authorization, or the PCM will come and get the Research Staff to speak with the patient directly.

4.2. Consent Processes:

Informed Consent and HIPAA authorization will be sought in advance from each prospective subject and appropriately documented in accordance with 32 CFR 219.117. Potential candidates will be notified about the study either through posted advertisements or by their care provider and will be given the opportunity to consent by one of the referred study coordinators. The study coordinator will provide a written copy of the Informed Consent Document (ICD). The subject may decline to consent without prejudice. At the subjects' discretion, they may take the ICD home to discuss further prior to making a decision. If the subject consents, a copy of the ICD will be given to the subject. No vulnerable populations are included in this research study. Subjects who cannot provide Informed Consent will not be allowed to participate. No Legally Authorized Representatives (LAR) will be utilized. Some subjects may be patients of the Investigators; however, the Investigators will have the study coordinators recruit their subjects to prevent any misconception of coercion or undue influence.

4.3 Participation Compensation: Subjects will not be paid for participation in this study.

4.4. Assent Process: N/A

4.5. Benefits:

There may be no direct benefits to the subjects for participating in this study. However, patients may benefit from a reduction in pain.

4.6. Risks:

The potential risks to participate in this study are minimal. There is a risk of inadvertent breach of confidentiality. The risks of battlefield auricular acupuncture associated with participating in this research study include:

LIKELY: Likely and not serious:

- Pain at insertion site
- Bleeding
- Flare of signs or symptoms (i.e. post-partum pain)

LESS LIKELY: Less Likely and not serious:

- Infection

4.7. Costs: N/A

4.8. Safeguards for Protecting Information:

The research consents will be stored in a locked cabinet in a locked room. Medical records will be annotated with ICD-10 code Z00.6 to reflect the subject's participation in a research study. All research data including patient demographics will be kept in an electronic database, which will be encrypted, double password protected and the access will be restricted. The research

data will be de-identified and any links to identifiable data will be destroyed as soon as possible. The research data will not be utilized for further research activity beyond the protocol stipulations without additional IRB approval.

4.9. Safeguards for Protecting Subjects:

The principal investigator will be responsible for the protocol safety monitoring. The PI will make study documents (e.g., consent forms, data pulls) and pertinent hospital or clinical records readily available for inspection by the local IRB and oversight staff for confirmation of the study data.

4.9.1. Minimizing Risks:

These risks will be minimized by cleaning the acupuncture site with an alcohol swab prior to placement. If at any time the patient reports a side effect, they will be referred to one of the Investigators for care.

4.9.2. Vulnerable Populations:

This research will not involve any treatment decisions related to the pregnancy or viability of the nonate, and if such questions come up, the Principle Investigator (PI) will refer the subject to their Primary Care Manager (PCM) and will not participate in any pregnancy or neonate-related decision making or guidance.

4.9.3. Clinical Care:

All subjects will receive standard of care regardless of inclusion into this study. If at any time a subject experiences any injury or adverse effects, appropriate clinical care will be given or subject will be referred to appropriate provider.

4.9.4. Injury Compensation: N/A

4.9.5. Data Safety Monitoring:

The trial will be conducted in compliance with this protocol, International Conference on Harmonization (ICH) Guidelines for Good Clinical Practice (GCP), and any applicable national and international regulatory requirements. The principal and associate investigators will be monitoring all aspects of the study in accordance with the appropriate regulations and will have regular meetings with periodic quality control of data documentation and collection. The objectives of the monitoring meetings will be:

- 1) To verify the prompt reporting of all data points, including reporting Serious Adverse Events (SAEs) and checking availability of signed informed consent,
- 2) To compare individual subject records, data pulls and/or the study source documents/case report forms (supporting data, laboratory specimen records and medical records to include physician progress notes, nurses' notes, subjects' hospital charts),
- 3) To ensure protection of study subjects, compliance with the protocol, and accuracy and completeness of records.

The principal investigator will be responsible for the protocol safety monitoring. The PI will make study documents (e.g., consent forms, data pulls) and pertinent hospital or clinical records readily available for inspection by the local IRB and oversight staff for confirmation of the study data.

5.0. Alternatives: The only alternative is not to participate in this study.

6.0. Data Analysis:

6.1. Outcome Measures:

Does battlefield auricular acupuncture provide significant pain control for mothers in the immediate post-partum period?

- Pain reduction by at least 50%
- Pharmacological pain control reduction
- Satisfaction with pain management in the immediate post-partum period

6.2. Sample size estimation/power analysis:

We are planning a study of a continuous response variable from matched pairs of study subjects. Prior data indicate that the difference in the response of matched pairs is normally distributed with standard deviation 4. If the true difference in the mean response of matched pairs is 2, we will need to study 33 pairs of subjects to be able to reject the null hypothesis that this response difference is zero with probability (power) 0.8. The Type I error probability associated with this test of this null hypothesis is 0.05.

6.3. Statistical Analysis: We will use a ROC analysis using pain scores collected and repeated measures of ANOVA will be used.

6.4 Number of Subjects:

Number of subjects planned for Nellis	Enrolled in Study	90	to result in	66	completing the study.
---------------------------------------	-------------------	----	--------------	----	-----------------------

TOTAL NUMBER OF SUBJECTS (nation-wide/study-wide): 90

7. Duration of Study: Approximate duration of the study: 2 years**8. Local and External Support Services:** None**9. Intramural (GME) and Extramural Funding Support:** None**10. Conflict of Interest:** No financial, personal, or off duty employment conflicts of interest exist.**11. Use of an Investigational New Drug, use of a Drug for a non-FDA approved purpose, use of an investigative device or use of a placebo:**

This research uses an Investigational New Drug YES NO
 This research uses a FDA approved drug for a non-FDA approved purpose YES NO
 This research uses an Investigational Device YES NO
 This research uses a placebo. YES NO

12. Medical Research Area for the Study: (Pick as many as appropriate)

 Analytical Chemistry	 Anatomy	 Anesthesiology	 Biochemistry
 Cardiovascular Surgery	 Cardiology	 Cell Biology	 Dentistry
 Dermatology	 Dietetics	 Electrophysiology	 Endocrinology
 Emergency medicine	 Gastroenterology	 General Surgery	 Hematology
 Histology	 Immunology/Allergy	 Infectious Disease	 Microbiology
 Molecular Biology	 Neonatology	 Neurology	 Neurosurgery
 Nursing	 OB/GYN	 Occupational Medicine	 Occupational Therapy
 Oncology	 Ophthalmology	 Oral/Maxillofacial Surgery	 Orthopedics
 Pathology	 Pediatrics	 Pharmacology	 Physical Therapy
 Mental Health	 Radiology/Imaging	 Urology	 Wellness
 Other (state):			

13. Attachments:

1. Form A: Certificate of Compliance
2. Form A1: Study Personnel
3. Informed Consent Document
4. HIPAA Authorization Document
5. Use of an Investigational Device in Research
6. BFA Discharge Instructions
7. Recruitment: Advertisement

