2.1. Associate Investigators (AI): See form A2 Study Personnel

2.2. Research Assistants (RA) & Coordinators (RC): See form A2 Study Personnel

2.3. The research relevance of this protocol focuses on:

Diagnosis Treatment Medical Utilization/Managed Care Prevention Medical Readiness Other

2.4. Location(s):

- Collaborating Facilities: N/A
- Air Force Sites seeking Regional IRB: [name], [contact]
- List study sponsors: N/A

3. Research Plan:

3.1. Purpose:

The purpose of this study is to compare battlefield auricular acupuncture plus standard of care versus standard of care in the reduction of pain, use of pharmacological analgesics, and satisfaction with experience in mothers in the immediate post-partum period.

3.2. Hypotheses, Research Questions or Objectives:

Does battlefield auricular acupuncture provide significant pain control for mothers in the immediate post-partum period?

3.3. Significance:

If effective, battlefield auricular acupuncture techniques can be used as a safe method of pain control in the immediate post-partum period and result in greater satisfaction with the labor and delivery experience as well as reduce complications associated with increased pharmacological interventions.

3.4. Military Relevance:

This research will directly benefit the healthcare of active duty members and beneficiaries who undergo delivery in the DoD healthcare system. Given the cost savings in avoiding pharmacological medications or other invasive interventions, this study may also provide long-term health care cost savings and improve mission efficiency.

3.5. Background and Review of Literature:

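### The analysis section (6.3) specifies no between-arm comparison for the listed pain outcome, analgesic use or satisfaction, and leaves the ROC target and the ANOVA outcome, effect and period unstated

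*Combined protocol and SAP*

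**What the plan says.** The whole of section 6.3 reads: "We will use a ROC analysis using pain scores collected and repeated measures of ANOVA will be used". No other part of the document adds an analysis.

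Section 6.1 lists three outcomes and designates none as primary. The pain outcome is "Pain reduction by at least 50" per cent; the others are reduced use of analgesic drugs and satisfaction with pain management. Section 3.1 states the aim as a comparison of two arms: "The purpose of this study is to compare battlefield auricular acupuncture plus standard of care versus standard of care in the reduction of pain", and it names analgesic use and satisfaction alongside pain.

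Section 6.2 sizes the trial on something else: "We are planning a study of a continuous response variable from matched pairs of study subjects", with a mean difference of 2, an SD of the difference of 4, and 33 pairs. Section 6.4 expects 66 of 90 enrolled women to complete.

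Pain is rated 0-10 at Visit 1, daily in hospital, and daily after discharge until 10 days after Visit 1 (section 3.6). Section 3.6.5 counts up to 11 questionnaires. Section 3.6.1 also singles out particular contacts: "After delivery of the battlefield acupuncture and the first post-hospital discharge day, the patient will be contacted by the research coordinators".

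**The concern.** An analyst handed section 6.3 could not tell which result answers the trial's question. The ROC has an input, the pain scores, but no state to be classified. The ANOVA could be run on any of several variables, could be judged on the group effect or on group-by-time, and could cover any stretch of the follow-up. The responder outcome, the only pain outcome listed, has no test at all and no named baseline. Analgesic use and satisfaction are not mentioned.

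Two things are at stake. The trial could finish without a planned between-arm result for any outcome it lists. And effect, period and baseline would be chosen later, when the choice could decide significance. The document is dated 5/29/2018, after the study period given in section 3.6.4, "June 2015 through June 2017", so data may already exist when those choices are made.

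**Working it through.** **1. The plan's own figure.** Inputs from section 6.2: difference 2, SD of difference 4, alpha 0.05 (two-sided reproduces the result), power 0.8. n = (4 × (1.960 + 0.842) / 2)² = 31.4, so 32 pairs by the normal formula. The paired t calculation gives 33.4, with power 0.795 at 33 pairs. The stated 33 reproduces. It concerns a paired mean difference, so it supplies no analysis of a responder proportion between two arms.

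**2. Outcomes set against analyses.**

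| Listed in 6.1 | Between-arm analysis in 6.3 |
|---|---|
| Pain at least halved (responder) | None; baseline and time point also unnamed |
| Analgesic use | None |
| Satisfaction | None |

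Candidate baselines for the responder outcome are:
- the entry score of 4 or more (section 3.6.7);
- nurse-charted scores from before treatment (section 3.6.1, "standard of care items: RN Recorded Pain assessments");
- the Visit 1 score. It is listed under the same visit as "Subject will be given treatment according to their randomization group", without saying whether it comes before or after treatment.

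**3. Does the unstated ANOVA effect matter?** Assumed: 33 per arm, 11 contacts, compound symmetry with correlation ρ, a 2-point effect at k contacts and zero elsewhere, and two-sided 5%. The per-woman SD is 4/√2 = 2.83 if the 4 in section 6.2 is the SD of a difference between independent women, or 4 if it is a per-woman SD.

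- Group main effect: mean difference 2k/11, SD of a woman's mean = SD × √((1 + 10ρ)/11), two-sample t on 64 df. For k = 3 the difference is 0.545; for k = 10 it is 1.818.
- Group-by-time: noncentral F on 10 and 640 df, λ = (33/2) × Σ(d_t − mean d)² / (SD² × (1 − ρ)). The sum is 4k(11 − k)/11, which is 8.727 for k = 3 and 3.636 for k = 10. Example: k = 3, SD 2.83, ρ = 0.3 gives λ = 16.5 × 8.727 / (8 × 0.7) = 25.7.

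Power (%) at ρ = 0.3 / 0.5 / 0.7:

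| SD | Contacts with effect | Group main effect | Group-by-time |
|---|---|---|---|
| 2.83 | 3 | 24.9 / 18.1 / 14.8 | 95.8 / 99.5 / >99.9 |
| 2.83 | 10 (none at Visit 1) | 98.9 / 93.6 / 85.4 | 57.1 / 75.2 / 95.2 |
| 4 | 3 | 14.8 / 11.4 / 9.8 | 67.0 / 84.2 / 98.2 |
| 4 | 10 (none at Visit 1) | 85.4 / 69.2 / 56.9 | 28.3 / 40.1 / 65.4 |

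For a brief effect, group-by-time has far more power throughout. For a long one, the main effect has more at ρ = 0.3 and 0.5, and group-by-time has more at ρ = 0.7.

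**4. One named contact, if the effect is present there.** The unadjusted two-sample t has 80.8% power (SD 2.83) or 51.6% (SD 4). With baseline adjustment, residual SD = SD × √(1 − ρ²): 84.3 / 90.4 / 97.7% (SD 2.83) or 55.5 / 63.7 / 80.0% (SD 4).

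**5. Responder outcome at 33 per arm.** Power = Φ{[|p1 − p0| × √33 − 1.96 × √(2p̄(1 − p̄))] / √(p0(1 − p0) + p1(1 − p1))}. The document gives no responder rates. With assumed control rates of 20%, 30% and 40%, 80% power is reached at 52.6%, 63.8% and 73.6%, a difference of about 33 points.

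**6. Missed contacts.** 90 − 66 = 24, and 24/90 = 26.7%.

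**The case against.** Several stronger readings are tempting, and the document does not support them.

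- *The ROC cannot give a treatment effect.* It could. If study arm were the state, the AUC would be the probability that a score in one arm exceeds a score in the other. What can be said is that the target is unstated.
- *The ANOVA tests mean pain, and no arm difference with an interval can come out of it.* Section 6.3 names no outcome for the ANOVA and says nothing about reporting. Group-by-time on pain scores is a fair reading given section 3.1, but it is a reading, and under it the responder outcome still has no test.
- *The better-powered effect always switches with how long the benefit lasts.* It does not at correlation 0.7, where group-by-time leads in both patterns.
- *The responder outcome is the primary because it is listed first.* Section 6.1 designates no primary.
- *Dropping incomplete cases costs planned power.* The 66 expected completers are exactly the planned 33 pairs. The risk is selection bias, and the 27% applies only if completing means answering every contact, which is not defined.
- *The dates show that results had been seen.* They show only that data may exist.

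A further objection is that the power ranges rest on compound symmetry and an all-or-nothing effect. This stands. Under AR(1) correlation of 0.5-0.7 with a Greenhouse-Geisser correction, group-by-time power for the 3-contact effect is about 80% (SD 2.83) or 46% (SD 4). Likewise, the adjusted figures for a named contact assume that baseline correlates with follow-up as contacts do with each other. Requiring an entry score of at least 4 truncates baseline and would tend to weaken that correlation. The fair comparator for the unadjusted ANOVA figures is 81% (52%).

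Finally, a smaller repair would close the textual gap: name the ANOVA's outcome, effect and period, and add a test of two proportions. That would still drop women with a missed contact and would not by itself give an effect size at a stated time.

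**Conclusion.** The point holds and must be fixed. Followed as written, the plan contains no specified between-arm analysis of any outcome in section 6.1, although section 3.1 makes those comparisons the purpose. This conclusion rests on the text alone. On the most generous reading of the ANOVA, the responder outcome still has no test and no baseline, and analgesic use and satisfaction still have no analysis.

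The power figures are illustrations. They show that the unstated choice between group and group-by-time can decide significance: for a 3-contact effect the two differ by more than 50 percentage points at every correlation and SD tried under compound symmetry. The exact values depend on that structure, on equal arms of 33, and on the assumed effect pattern.

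**What to change.** Replace section 6.3 with the following.

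- **Pain score.** A linear mixed model for 0-10 pain with arm, day, arm-by-day, pre-treatment pain and delivery mode, in all randomised women with any follow-up, analysed as randomised. Report the adjusted arm difference with 95% CI at one named early contact after Visit 1, for example the first daily contact.
- **Responders.** At the same contact, the between-arm difference in the proportion whose pain at least halved, with 95% CI. Use one named pre-treatment baseline (the entry score, the last nurse-charted score before treatment, or the Visit 1 score if taken before treatment) and one stated rule for missing scores.
- **Secondary.** Arm differences with 95% CI for analgesic use, satisfaction and pain on other days.
- **ROC.** Drop it, or keep it as exploratory with a stated target.

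State in section 6.1 which pain measure is primary, and document that it was chosen without sight of arm-level results. If those have been seen, keep the listed 50% outcome as the pain outcome and label any change post hoc.

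**Cost.** Sections 6.1 and 6.3 are rewritten, and standard software suffices. No new data are needed if an entry score or a pre-treatment nurse score was recorded; otherwise the timing of the Visit 1 score has to be established. One measure and one contact then rank above the rest. A mean-score primary fits the continuous sizing in section 6.2 but, at one contact without adjustment, has 81% power (52% if the SD is 4). Adjustment raises that only as far as baseline predicts follow-up. A responder primary needs about a 33-point difference at this size. If benefit is brief, group-by-time may have more power than the named contact, but it gives neither the size nor the direction of the effect.

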NCT02526186

Document date: 5/29/2018

Battlefield Auricular Acupuncture for Control of Post-partum Pain

PROTOCOL FOR CLINICAL INVESTIGATION – NON-EXEMPT HUMAN PROTOCOL SUMMARY

1. Title:

Battlefield Auricular acupuncture for control of post-partum pain.
FWH20150072H

2.0. Principal Investigator (PI):

PI:	
Name	[name]
Rank/Corps or Civilian Rating	Col
Date of IRB Approved CITI Training & Date of Good Clinical Practice Training	12/28/17
Branch of Service	USAF
AD Mil/DoD Civilian/Ctr/Non-DoD Civ	AD Mil
Department & Base	Family Medicine Residency, Nellis AFB
Phone & [contact]
E-Mail Address & AKO/DKO E-Mail Address	[contact]

3.0. Research Plan:

3.1. Purpose:

The purpose of this study is to compare battlefield auricular acupuncture plus standard of care versus standard of care in the reduction of pain, use of pharmacological analgesics, and satisfaction with experience in mothers in the immediate post-partum period.

3.2. Hypotheses, Research Questions or Objectives:

Does battlefield auricular acupuncture provide significant pain control for mothers in the immediate post-partum period?

4. Brief Summary of the study:

We will conduct a randomized controlled trial to determine whether the addition of battlefield auricular acupuncture to standard of care is effective for control of postpartum pain for mothers in the immediate post-partum period. Post-partum patients (DoD beneficiaries) 18 years or older, regardless of gravida/parity, who plan to have a childbirth in a hospital setting will be offered the opportunity to participate in the study through PCM referrals and posted advertisements. After a minimum of 6 hours post-vaginal delivery or 24 hours post caesarean section subjects will be given treatment according to their randomization group. Subjects will be assessed on pain control, overall satisfaction with pain management, and the amount of pharmacological pain medications used. Safety of measures will also be assessed to include infection rates, syncope, vertigo, and hypotension.

5. Subjects:

Post-partum females (DoD beneficiaries). Age 18 years or older, will be recruited at the Mike O'Callaghan Military Medical Center. No other special populations (e.g., children, military basic trainees, prisoners, detainees) will be recruited.

6. Inclusion/exclusion criteria:

Inclusion:

- Post-partum female (DoD beneficiaries).
- Age 18 years or older
- Pain score rating post-delivery of greater or equal to 4/10.

Exclusion:

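### Repeated-measures ANOVA is the only longitudinal method named, with up to 11 pain contacts and 24 of 90 women planned not to complete; a mixed model would use every available score at little cost

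*Combined protocol and SAP*

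**What the plan says.** Section 6.3 is a single sentence. It names ROC analysis, which is not longitudinal, and adds that "repeated measures of ANOVA will be used". It gives no model terms, covariates, analysis population, list of contacts or rule for incomplete records, and no other section does.

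The data are clearly longitudinal. Section 3.6 asks for pain (0 to 10) at Visit 1. It then says "Data will be collected each day until the patient has been discharged from the hospital", and for the period after discharge "Each day up until 10 days post Visit 1". Section 3.6.1 adds that "Post-hospital discharge follow-up will continue for up to 10 days post Visit 1 for each study group". The procedures table in 3.6.5 allows up to 11 questionnaires per woman, which fits Visit 1 plus 10 daily contacts.

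Section 6.4 enrols 90 women so that 66 end up "completing the study". The reasons for the expected loss are not given. The protocol summary (section 4) says that women "who plan to have a childbirth in a hospital setting will be offered the opportunity to participate", and entry requires a post-delivery pain score of at least 4. Some women could therefore leave before Visit 1, where "Subject will be given treatment according to their randomization group".

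The comparison is standard care with or without added needles, and placebo is marked not applicable. Section 3.6.1 already records "delivery method (either Caesarean section or spontaneous vaginal delivery").

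**The concern.** Classical repeated-measures ANOVA needs a complete record. If it is run that way, one missed call removes a woman and all her other scores. Recently delivered mothers who are phoned daily will plausibly miss calls.

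Two things are at stake. The first is precision, because partial records are thrown away. The second is bias. Women know their arm, so whether they stay reachable could depend on pain differently in the two arms, and women with complete records would then no longer be a fair comparison.

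Leaving out pre-treatment pain and delivery method is a smaller matter: it costs precision, not validity.

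**Working it through.** **The plan's own figures.** For 33 pairs: n = ((1.960 + 0.842) × 4/2)² = 31.4, or 32 by the normal approximation. The iterated t version gives 33.4, and exact power at 33 pairs is 0.795. The stated 33 pairs (66 women) therefore reproduces. Planned non-completion is (90 − 66)/90 = 26.7%.

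**Women left if every included contact is required** (miss rates are assumptions, not in the plan). With independent misses the count is 90 × (1 − m)^T:

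| Contacts T | m = 5% | m = 10% |
|---|---|---|
| 11 | 51.2 | 28.2 |
| 10 | 53.9 | 31.4 |
| 3 | 77.2 | 65.6 |

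The miss rate that by itself leaves 66 of 90 is 1 − (66/90)^(1/11) = 2.8% for 11 contacts and 3.1% for 10. The three-contact row is included because the plan does not say which contacts enter.

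If misses cluster within women, a beta-binomial model applies: P(no miss) = Π (b + i)/(a + b + i), for i = 0 to T − 1, with s = 1/ρ − 1, a = m·s and b = (1 − m)·s. With 11 contacts and ρ = 0.1, 0.3, 0.5, the women left are 61.5, 71.6, 77.2 at 5% and 41.5, 56.6, 66.0 at 10%.

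**Standard error, mixed model against completers.** Assumptions: 45 per arm, 10 days, loss at random, difference averaged over days, known covariance (compound symmetry 0.4 or 0.6, or a random-intercept share of 0.4 or 0.6 plus AR(1) 0.5). The completer variance is c′Sc/n_complete. The mixed-model variance is c′[Σ A′(ASA′)⁻¹A]⁻¹c, where A picks out the scores each woman has.

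| Assumed loss | Mixed-model SE smaller by |
|---|---|
| All 24 stop during follow-up | 12% to 13% |
| Half of the 24 have no post-treatment score | 6% to 7% |
| None of the 24 has a post-treatment score | 0% |
| 5% missed, clustered (ρ 0.1 to 0.5) | about 6% to 16% |
| 5% missed, independent | 22% to 24% |
| 10% missed, clustered (ρ 0.1 to 0.5) | about 12% to 30% |
| 10% missed, independent | 41% to 44% |

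As a check on the first row, if all 24 had given every score the gain would be 1 − √(66/90) = 14.4%, so 12% to 13% is near the ceiling. The gain depends on the contrast. With 11 contacts and correlation 0.3 to 0.7, the effective number per arm rises from 33 to about 42 to 44 for the average, but only to about 35 to 40 for day 10, where 1 − √(33/35) = 3% and 1 − √(33/40) = 9%.

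**Bias, as illustration only.** Dropout is assumed to depend on the last recorded score.
- *Same direction in both arms, true effect 2 points:* completer bias is 0.06 to 0.18 points (3% to 9% of the effect); the mixed model's is at most about 0.02.
- *Opposite directions by arm, odds ratio 1.28 per point, no true effect, 66 of 90 completing:* completer bias is 0.26 to 0.80 points with 12% to 31% false positives; the mixed model's is at most 0.04 with about 5%.
- *Dropout on the unseen current score:* mixed-model bias is 0.05 to 0.16 against 0.25 to 0.79 for completers.

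The false-positive rates come from a mixed model with no covariates, tested with t on 88 df instead of Kenward-Roger, so they are not a test of the exact model proposed below.

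**The case against.** The strongest reply is that the plan names a family of methods, not an algorithm, and nowhere says that incomplete records are dropped. That stands: the harm is conditional on the classical form being run. What the documents do show is silence on missing scores, which leaves the choice open until the data are seen.

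A reader might infer that loss of 24 women leaves the trial short of its target. The documents do not support this. Section 6.4 inflates enrolment so that 66 complete, which is the number in 6.2, and a completer analysis falls below it only if completers also miss contacts. Inflation does not, however, protect the comparability of the arms.

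A reader might also take the counts of 28 to 54 women, or gains of 22% to 44%, as expected results. They require all 10 or 11 contacts and independent misses. With three contacts, 77 and 66 women remain. With clustered misses the gains are much smaller. Contacts in hospital may be in person and nurse-recorded pain is also collected, so an equal miss risk at every contact is doubtful.

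Nor do the documents support dropout in opposite directions by arm or an odds ratio of 1.28. The bias of up to 0.80 points shows what could happen and does not forecast it.

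**Conclusion.** The point holds as a cheap improvement. It is certain that the only longitudinal method named is one whose classical form discards incomplete records, in a plan with up to 11 contacts and 26.7% planned non-completion, and that no missing-data rule is given.

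The size of the benefit is not certain. It runs from nothing, if the 24 have no post-treatment scores and nobody else misses a call, to a substantial gain in precision if missed calls are common and scattered. Bias from a completer analysis is possible because the comparison is open-label, but its direction and size rest wholly on assumed dropout. It would be wrong to conclude that repeated-measures ANOVA is invalid here or that the result will be biased. A mixed model cannot recover women who leave before giving a post-treatment score, and it is not immune when dropout depends on unseen pain.

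**What to change.** Replace the ANOVA in 6.3 with:

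> Pain scores (0-10) will be analysed with a linear mixed model including all randomised women, by assigned group, with at least one post-treatment score, using every available post-treatment score. Fixed effects: group, day (categorical), group by day, pre-treatment pain score and delivery method. Covariance: random intercept for woman plus AR(1) residuals, with Kenward-Roger standard errors. A sensitivity analysis will shift missing scores by a range of values separately in each arm.

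State also that the covariate pain score is recorded before treatment; the Visit 1 text does not say whether its score comes before or after.

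This should not bring in a new primary result. The sponsor should name in advance which group contrast, a given day or an average, answers the study question. The 50% pain reduction outcome in 6.1 is not covered by this change and needs its own analysis.

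The covariance is chosen because it contains both simpler forms. AR(1) alone, fitted to compound-symmetric data in the opposite-direction illustration, left a bias of 0.06 to 0.19 points, against at most 0.02 for random intercept plus AR(1). An unstructured form would need 10 × 11/2 = 55 to 11 × 12/2 = 66 parameters.

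The cost is one paragraph, slightly more analysis work, and no new data beyond fixing when the covariate score is taken. The downside is reliance on missing-at-random and on the chosen covariance; the sensitivity analysis addresses the first of these.
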